3. Exploratory Aim: Describe the pharmacological and non-pharmacological strategies Veterans are using to manage pain and their perceived helpfulness. This will provide insights into the effects of the current opioid restrictions on pain management strategies. These strategies & their perceived helpfulness will be assessed using the Pain Management Strategies Survey at baseline, 6 weeks, 3, and 6 months.

Study Design

The proposed study is a multi-site, double-blind, two-arm, parallel, randomized controlled trial. At-risk Veterans will be randomly assigned to one of two groups: 1) Acceptance and Commitment Therapy (ACT); or 2) Attention Control (AC). Primary and secondary outcomes will be measured at 6 weeks, 3 and 6 months but 6 months will be the primary outcome endpoint for determining mediator effects. Data collected at postoperative week 1 will be used as potential moderators of treatment response.

Schema

Inclusion and Exclusion Criteria

The target study population is veterans undergoing unilateral total knee arthroplasty (TKA) who are at-risk for persistent postsurgical pain (i.e. report moderate to severe preoperative pain in the presence of anxiety and/or depression OR report severe pain and absent anxious and depressive symptoms). A total of 430 participants (215 per group) will be recruited to achieve 150 subjects per group.

Inclusion Criteria

Participants must meet all the following inclusion criteria to participate in this study:

- Veteran;
- 18 years old or older;
- Having unilateral total knee arthroplasty (TKA);
- At risk for pain, anxiety, depression and/or stress, or pain catastrophizing defined as 1, 2, 3 or 4 (below):
 1. Worst pain greater than or equal to 7 on BPI (severe pain)
 2. Worst pain 3-6 (moderate to severe pain) on BPI AND anxiety symptoms (anxiety score greater than or equal to 6 on the DASS 21 or DASS stress score greater than or equal to 10)
 3. Worst pain 3-6 (moderate to severe pain) on BPI AND depressive symptoms (depression score greater than or equal to 7 on the DASS 21)
 4. Worst pain 3-6 (moderate to severe pain) on BPI AND PCS score greater than or equal to 20

Exclusion Criteria

All candidates meeting any of the exclusion criteria will be excluded from study participation.

Exclusion criteria are:

- Inability to complete study forms because of language/literacy barrier;
- Bipolar or psychotic disorder;
- History of brain injury (moderate to severe TBI, other severe injury);

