For the exploratory aim, frequencies for each pharmacologic and non-pharmacologic pain management strategy will be calculated to describe the types of strategies reported at each visit. Patterns (from baseline to 6 months) and trends (i.e. changes over the 4 year data collection period) will be examined. Helpfulness ratings will be averaged using means and standard deviations or medians and interquartile ranges for each strategy to provide insights on strategies at-risk Veterans find helpful. Differences in types and helpfulness of pain management strategies by treatment group will be explored.

Sample Size

Sample size was estimated using KOOS-Activities of Daily Living Subscale (the primary outcome requiring the largest sample size). According to the literature, a change of 8 points or more represents a clinically significant improvement.⁸⁵ Therefore, assuming an average of 6 participants per workshop (cluster), with an ICC of 0.06 and a standard deviation of 18, a sample size of 300 Veterans (n=150 per treatment group) will be needed to detect a clinically

significant difference of 8 at a 0.0167 significance level (adjusted for testing at 3 time points) with 0.80 power. Assuming 20% will have surgery cancelled/postponed due to health issues and 10% will drop out after randomization (17% and 10%, respectively, was observed in our R34 study), we plan to enroll 430 Veterans to ensure that we will have $n=150$ per treatment group for the primary aim analyses. Veterans who do not have surgery after randomization will be followed over a similar timeframe and will be included in the secondary analyses.

Recruitment, Consent and Enrollment

Summary of recruitment and consent process, in-person

Identifying Patients

In order to increase awareness of the study, flyers describing the study will be posted in the orthopedics clinic and copies will be made available for patients to take. The study's Research Assistant (RA) will use Vista to identify all patients scheduled in the VAMC Orthopedics Clinic for a knee pain consultation. The RA will then review these patients' medical records to determine if they speak English with adequate competence AND do not have a diagnosis of dementia, bipolar or psychotic disorder, or history of brain injury. They will also review prior orthopedic notes to gauge readiness for surgery.

Approaching Patients

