Consented participants will be asked to complete the Agreement to Participate; Demographics, SCQ, BPI, PCS and DASS 21. This should take 20-30 minutes. Participants who meet inclusion criteria (Worst pain greater than or equal to 7 on BPI [severe pain]; OR worst pain 3-6 [moderate to severe pain] [on BPI AND anxiety symptoms [anxiety score greater than or equal to 6 on the DASS 21 or DASS stress score greater than or equal to 10]; OR worst pain 3-6 [moderate to severe pain] on BPI AND depressive symptoms [depression score greater than or equal to 7 on the DASS 21]; OR worst pain 3-6 [moderate to severe pain] on BPI AND PCS score greater than or equal to 20) will then be instructed to complete a set of surveys (i.e., OQ-45.2; CAGE; DAST-10; PCL-5; KOOS - baseline; STAI-Trait; PMSS (baseline); CPAQ; CPVI; PROMIS sleep: COVID impact). Completing these surveys should take approximately one hour. These surveys may be completed online on paper. The medical record will be reviewed for this same information (i.e. demographics, medical information, medications). Any discrepancies in medical information will be discussed with the participant to facilitate complete and accurate data. Once completed, participants will be scheduled for a workshop and asked to order their lunch (if attending an in-person workshop). Participants will also be given instructions for accessing the post-op surveys online through REDCap and given contact information for study personnel.

Participants who have completed the pre-randomization assessment will be considered “enrolled”.

Study Interventions

Veterans will attend either a 1-day ACT workshop or a 1-day AC workshop prior to surgery. These workshops may be held online via Zoom to minimize risk of exposure to COVID-19. Two psychotherapists, trained in ACT, will provide the workshops in groups of 3-10 Veterans. Each workshop will last 5-6 hours.

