At 6 weeks, 3 months and 6 months postop, all Veterans will receive REDCap automated survey invitations and, if they have consented to participate in the Department of Veterans Affairs' Annie mobile Short Message Service (SMS) text messaging, short text messages reminding them to take the survey. If participants prefer, paper copies of these surveys will be mailed to them with a cover letter. At 6 weeks, the survey will include: BPI; DASS-21; PCS; OQ-45.2; KOOS - postop; CPAQ; CPVI; Promise Sleep; Complications; and workshop usefulness (6wk). At 3 months, the survey will include: BPI; DASS-21; PCS; PMSS (postop); OQ-45.2; KOOS - postop; CPAQ; CPVI; and Promise Sleep. At 6 months, the survey will include: BPI; DASS-21; PCS; PMSS (postop); OQ-45.2; KOO - postop; CPAQ; CPVI; Promise Sleep; Workshop Usefulness (6mo); and COVID-19 Impact.

Survey Review

In each case, after the participant has completed the surveys, the RAs will cross-check the medications reported in the BPI and DASS-21 with those in the medical record and discuss discrepancies with the participant.

Data Collection and Quality Assurance

Data management

The Study Coordinator at the Coordinating Site will be responsible for:

1. Designing and maintaining the REDCap data collection site as well as the Tracking Database
2. Ensure all data is stored so that blinded study personnel do not have access to any data that would un-blind them.
3. Conduct regularly scheduled audits (including hard-copy-to-electronic-copy checks) and data quality checks

REDCap

All data collection forms will be available through a REDCap (Research Electronic Data Capture) database (supported by the institutional CTSA) and patients can directly enter data into these forms. They will enter data into a central database through their computer or a tablet provided in the clinic. This will eliminate error in data entry, and reduce time necessary for data entry, cleaning and analysis. Range checks will be programmed into the data entry system when the nature of the data allows so that it will not permit invalid values to be entered into the database.

When a data collection session is completed, the RA will review electronic forms for completeness and validity. The RA will resolve all queries and will enter an override for all values that have been confirmed as being accurate. Reports will also be run periodically to confirm or correct questionable values. All changes will be tracked through the REDCap audit trail.

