10. Recordings of workshops and fidelity ratings: (S:) IOW Services Drive\Research [name] Closed\PrePARE

Strategies for minimizing missing data

Strategies will include:

1. Reviewing all surveys for completeness before finalizing
2. Conducting weekly texts and/or phone calls, as needed, to remind participants to complete daily logs
3. Contacting participants postoperatively to review data entry requirements, provide them with verbal and written directions for filling out and submitting daily logs, reviewing contact information, and identifying appropriate methods/times for follow-up contacts.

Protocol Deviations

Protocol deviations will be entered in the study's Tracking Database are known to happen in order to compile an electronic log for reporting purposes.

Monitoring

Data will be routinely monitored at the time of data collection. REDCap will be used to collect data and the researchers will be prompted at the end of each session to check missing entries. Regular team meetings will be held where researchers can report ongoing data collection concerns to ensure proper adherence to the protocols and high-quality data collection.

Data Collection Instruments

Demographics/Medical Information

Description: Demographic information will be collected via a questionnaire including age, sex, race, ethnicity, marital status, education, and household income. Medical information on smoking, BMI, co-morbidities and all medications will also be collected from the medical record. For both demographic and medical information, the medical record will be reviewed, and discrepancies will be discussed with the Veteran and resolved to facilitate complete and accurate data. These variables will be used to characterize the sample and examine possible influences on treatment response.

Brief Pain Inventory Short Form (BPI-SF)

Outcome Measure: Pain (intensity)

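### The exploratory aim promises the Pain Management Strategies Survey at 6 weeks, but the 6-week survey list omits it, so strategy-level use and helpfulness at that visit would go unmeasured

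*Combined protocol and SAP*

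**What the plan says.** **The aim.** Under Objectives, the Exploratory Aim covers drug and non-drug strategies and their perceived helpfulness, and gives the timing: "perceived helpfulness will be assessed using the Pain Management Strategies Survey at baseline, 6 weeks, 3, and 6 months".

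**The analysis.** Data Analysis states that frequencies for each strategy "will be calculated to describe the types of strategies reported at each visit". It also plans patterns from baseline to 6 months, trends over the data collection period, helpfulness summaries, and an exploration of differences by treatment group.

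**The schedule.** The pre-randomization battery includes "PMSS (baseline); CPAQ; CPVI". The section on the 6-week, 3-month and 6-month surveys then gives one list per visit:

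- 6 weeks: "At 6 weeks, the survey will include: BPI; DASS-21; PCS; OQ-45.2; KOOS - postop; CPAQ; CPVI; Promise Sleep; Complications; and workshop usefulness (6wk".
- 3 months: the list opens "At 3 months, the survey will include: BPI; DASS-21; PCS; PMSS (postop", so the post-op form of the survey (PMSS) is included.
- 6 months: the post-op form is again included.

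**Two related statements.** Study Design says "Data collected at postoperative week 1 will be used as potential moderators of treatment response". The strategies for minimizing missing data include weekly texts or calls to "remind participants to complete daily logs".

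**The concern.** The aim and the visit schedule disagree about the first post-operative survey. The REDCap survey and its paper copy would naturally be built from the itemised lists, so the omission would carry through to the data. A response not collected at 6 weeks cannot be collected afterwards.

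The aim is meant to give insight into how opioid restrictions affect pain management after surgery. Without a 6-week wave, the analysis by visit has no strategy-level data at the earliest post-operative survey. The pattern from baseline to 6 months then goes straight from baseline to 3 months, and the exploratory arm comparison cannot be made at 6 weeks.

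The week-1 data and the daily logs raise a similar but weaker question. The protocol refers to both, and its readable text does not say when or with what instrument they are collected.

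**Working it through.** No figure in the plan needs reproducing. The check sets the sections side by side.

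**1. Waves promised and waves scheduled**

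| Time point | Exploratory Aim | Survey lists |
|---|---|---|
| Baseline | yes | yes |
| 6 weeks | yes | no |
| 3 months | yes | yes |
| 6 months | yes | yes |

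Promised: 4. Scheduled: 3. Of the 3 post-operative waves promised, 2 are scheduled. No other section places the PMSS at 6 weeks. The 6-week list reads as a complete sentence from its first instrument to its last, so text lost in PDF conversion is an unlikely explanation.

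**2. Can the 3-month form fill the gap?** The PMSS description says that the post-op form asks whether each strategy has been used since surgery and whether it is in use now, with a helpfulness rating from 0 to 4 after a yes. Take a strategy used at week 6 and dropped by week 10. At 3 months it appears as used since surgery and not in current use. The form shows that it was used at some time, but does not date that use to week 6. Any helpfulness rating is a later judgement, not the one that would have been given at 6 weeks. The 6-month form has the same limits.

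**3. Can the other 6-week data fill the gap?** Under Survey Review, after each survey the research assistants compare the medications reported in the BPI and DASS-21 with the medical record and discuss discrepancies with the participant. Both forms are in the 6-week list, so there is medication information at that visit. The descriptions of those two instruments mention neither non-drug strategies nor a helpfulness rating for each strategy.

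**4. How many participants?** At the analysis target of 150 per group, 2 × 150 = 300 participants would lack this wave.

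**5. What would adding it ask of participants?** The PMSS has 42 original items plus 10 added items: 42 + 10 = 52. If each item is one strategy with up to three responses (used since surgery, in use now, helpfulness), the ceiling is 52 × 3 = 156 responses. Most participants would give fewer, because helpfulness follows only a yes.

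**6. Week-1 data and daily logs.** The post-operative contacts that the text describes are a booster call two weeks after surgery, a conditional second booster, and the three surveys. No log appears in the survey lists, the data locations or the instrument descriptions. However, Data Analysis names perioperative variables, including pain and function on postoperative day 1, as possible covariates or moderators. The missing-data section also describes post-operative contact to explain how logs are filled out and submitted.

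**The case against.** A reader might infer that pain treatment at the first post-operative visit would go wholly unrecorded. The documents do not support that. Medications are reported and checked at 6 weeks, and the 3-month PMSS captures any use since surgery, although without a date. What is lost is narrower: current use and helpfulness by strategy at 6 weeks, mainly for non-drug strategies. Nor do the documents give any analgesic-use figure to show that 6 weeks is the most informative time.

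It can also be said that the omission was deliberate. The lists differ by visit (complications only at 6 weeks, COVID-19 impact only at 6 months among the post-op surveys), so a shorter 6-week battery is plausible. If so, the aim is what needs correcting. This objection stands in part: the documents do not show which section was intended. It does not remove the contradiction.

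A third objection is that the aim is descriptive, with no sample-size basis, and keeps three time points. That is correct, and it limits the weight of the point.

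Finally, a reader might infer that the week-1 moderator analysis has no data and that the sentence should be deleted. That goes too far. The survey section need not list every data source, the schema figure is not available in the text reviewed, and perioperative measurements are named elsewhere. The most that can be said is that the readable text does not explain how these data are obtained.

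**Conclusion.** The contradiction is real and worth correcting. If the survey lists govern, one of three promised post-operative PMSS waves will be absent for all participants, about 300 at the analysis target. The by-visit frequencies and helpfulness summaries would then have no PMSS data at 6 weeks. Later forms cannot restore them, and the medication cross-check covers only part of what the aim asks.

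The consequence stays within the exploratory aim. The BPI, KOOS, DASS-21, CPAQ and CPVI are all in the 6-week list, so the primary and secondary comparisons, including the 6-week mediators, are unaffected.

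The conclusion assumes that the itemised lists describe what is actually administered. If the 6-week REDCap survey already contains the form, only the protocol text needs correcting. The week-1 and daily-log references call for clarification and support no firmer conclusion.

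**What to change.** Reconcile the Exploratory Aim with the post-op survey lists in one of two ways.

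- **Preferred:** add the post-op PMSS to the 6-week REDCap survey and its paper copy, so that the aim can be answered as written. The form already exists and its recall period suits a 6-week visit. The cost is a form assignment, a minor amendment, and about 52 more items at that visit, some with follow-up responses.
- **Alternative:** remove 6 weeks from the aim and limit the by-visit analysis to baseline, 3 months and 6 months. This costs a text correction and gives up the early post-operative picture of non-drug strategies and helpfulness.

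If the form is added after some participants have passed 6 weeks, record the start date, report the number with 6-week data in each arm, and describe 6-week calendar trends only from that date.

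Separately, state when, how and with what instrument the week-1 moderator data and the daily logs are collected. Remove the references only if the study team confirms that these data are not collected. This costs a few sentences.

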- Cognitive impairment (documented in medical record and/or MIS-T score of less than 4);
- ACT therapy within the past year;
- Inability to attend workshop prior to surgery;
- Imminent risk of suicide (including recent, related hospitalization);
- Indicated surgery is revision of TKA

Termination

Participants will be terminated from the study if they do not have surgery within approximately one year of attending workshop

Re-approaching Potential Participants

Consented participants who do NOT meet inclusion criteria before their surgery may be rescreened, re-approached, re-consented and reassessed for eligibility if they are indicated to have a second TKA surgery before the end of the study enrollment period. These participants will be eligible for this reassessment no earlier than eight weeks after their first TKA.

Data Analysis

Descriptive statistics (means, medians, percentages, standard deviations, and inter-quartile ranges) of all variables will be computed for each intervention group. We will describe sex and race/ethnicity results separately to identify potential differences, based on these biological variables. The distributions of continuous variables will be evaluated for normality. If data are non-normal, statistical analyses appropriate for non-normal data will be utilized (see below). Variables will be compared across intervention groups using a t-test for continuous variables, Wilcoxon-rank sum test for ordinal and non-normally distributed continuous variables, and Pearson Chi-square test for categorical variables. Variables that are found to significantly differ between the groups will be used as covariates in the comparison of outcome measures between the treatment groups.

Intent-to-treat (ITT) analyses will be conducted to assess treatment efficacy on post-operative outcomes using all subjects that have been randomized and had surgery performed. Only those who receive surgery are included in these analyses to test the efficacy of ACT on the primary and secondary outcome measures because our underlying model for treatment effectiveness is based on the assumption that ACT will prevent the development of PPSP by helping Veterans cope with postoperative pain. Therefore, receipt of surgery is inherent in our treatment model. Follow-up data on randomized subjects that did not have surgery will be included in a secondary analyses that will contrast the effect of ACT between those with and without surgery.

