For variables in the primary aim (pain severity and functioning), efficacy of ACT compared to AC at 6 weeks, 3 months and 6 months will be tested using linear mixed model analysis for repeated measures. The fixed effect in the model will include intervention group, time, and intervention*time interaction effect. The model will also include site, workshop (cluster) within intervention, and subject as random effects. Test of mean contrast will be used to compare between treatment group means and mean change from baseline to 6 weeks, 3 and 6-months post-TKA between ACT and AC. P-values will be adjusted using Bonferroni's method to account for the number of tests performed. The efficacy of ACT versus AC will be expressed as the group mean difference with a 95% confidence interval (CI), using the SAS STAT (14.1) MIXED procedure.

For the secondary aim (A), efficacy of ACT compared to AC on anxiety symptoms, depressive symptoms, pain acceptance, and engagement in values-based behavior will be compared using linear mixed model for repeated measures. Intervention group mean differences will be estimated and tested as described in the analysis for the Aim1 variables.

For the primary and secondary aim analyses, it is expected that randomization will lessen the need for covariate or moderator adjusted analyses. However, if any demographic, baseline, time from workshop to surgery, or perioperative variables (i.e. perioperative anesthesia/analgesic, postoperative complications, postop day 1 pain and function, etc.) are found to differ between intervention groups, the model will be expanded to include these variables as covariates or effect moderators to estimate and test intervention group mean differences, or odds ratio, controlling for these variables.

In addition to the analyses described above for the primary & secondary outcome measures, similar linear mixed model analyses that include all randomized subjects will be performed. This secondary analysis will include surgery status in the model to contrast the impact of the intervention on those with and without surgery.

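### The only inferential route by which the demographic and medical variables can enter as effect moderators depends on an arm imbalance, which is unrelated to effect modification

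*Combined protocol and SAP*

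**What the plan says.** Under Data Collection Instruments, the Demographics/Medical Information entry lists age, sex, race, ethnicity, marital status, education, household income, smoking, BMI, co-morbidities and medications. It closes with their purpose: "These variables will be used to characterize the sample and examine possible influences on treatment response". No model, subset of variables or significance level is attached.

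The Data Analysis section has two rules that reach these variables:

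- A covariate rule: "Variables that are found to significantly differ between the groups will be used as covariates in the comparison of outcome measures". The screening tests are given as "Variables will be compared across intervention groups using a t-test for continuous variables", with rank-sum and chi-square tests for other variable types. None is described as accounting for workshop.
- A rule for the primary and secondary aim analyses. It starts from the premise that "it is expected that randomization will lessen the need for covariate or moderator adjusted analyses". It then says that if demographic, baseline, workshop-to-surgery time or perioperative variables "are found to differ between intervention groups, the model will be expanded to include these variables as covariates or effect moderators".

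Three statements about differences in response carry no imbalance condition:

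- Data Analysis, on sex and race/ethnicity: "We will describe sex and race/ethnicity results separately to identify potential differences, based on these biological variables".
- Study Design: "Data collected at postoperative week 1 will be used as potential moderators of treatment response".
- Data Analysis, on surgery status: "This secondary analysis will include surgery status in the model to contrast the impact of the intervention on those with and without surgery".

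**The concern.** The second Data Analysis rule uses one trigger for two different jobs. A baseline imbalance can be a reason to consider adjusting the group comparison. It is not a reason to suspect that the ACT effect depends on that variable. Randomisation makes the distribution of age or BMI similar in the two arms on average. It does not make ACT work equally well at every age or BMI. So randomisation does not lessen the need to look at moderators, and a lack of imbalance is no evidence against moderation.

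For pre-randomisation variables the trigger therefore selects by chance. A true moderator that happens to be balanced is passed over, and an irrelevant variable that happens to be imbalanced may be fitted as a moderator. Even a variable that meets the trigger may enter only as a covariate, because the clause leaves that choice open.

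At stake is how any statement about who responds to ACT is read. An interaction that was never fitted could be taken as absent, and one fitted after a chance imbalance could be over-interpreted. The point does not concern which covariates adjust the primary estimate.

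**Working it through.** **The plan's own figure.** The documents give no figure for any moderator analysis, so the check starts from the Sample Size section: 6 per workshop, ICC 0.06, SD 18, difference 8, level 0.0167, power 0.80, 150 per arm.

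- Design effect: 1 + (6 − 1) × 0.06 = 1.30.
- The two-sided normal approximation gives 138 per arm.
- A t-test on 2(k − 1) degrees of freedom, with k workshops per arm, gives power 0.791 at k = 24 and 0.811 at k = 25. The smallest adequate design is 25 × 6 = 150 per arm, which matches the plan.
- Enrolment: 300 / (1 − 0.30) = 429, against 430 stated.

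The planning inputs are therefore used below as they stand.

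**Chance that a given pre-randomisation variable meets the trigger.** The screening level is not stated; 0.05 two-sided is assumed. The workshop ICC of baseline variables is not stated either; 0 to 0.06 is assumed, with 0.06 borrowed from the sample-size calculation. A test that ignores workshop flags a variable with probability 2 × (1 − Φ(1.96 / √DE)), where DE = 1 + 5 × ICC.

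| Baseline ICC | DE | Probability flagged | Simulated |
|---|---|---|---|
| 0 | 1.00 | 0.050 | 0.049 |
| 0.06 | 1.30 | 0.086 | 0.088 |
| 0.10 | 1.50 | 0.110 | not run |

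The simulation used 25 workshops of 6 per arm and 20,000 runs. Whether the variable modifies the treatment effect does not enter the formula.

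**How many variables would be examined.** Leaving out sex, race and ethnicity, which have their own descriptive statement, the entry lists 8 items: age, marital status, education, income, smoking, BMI, co-morbidities and medications. The last two are composites, so the count is approximate.

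- Expected number flagged: 8 × 0.050 = 0.40 to 8 × 0.0856 = 0.69.
- Chance that none is flagged, if independent: 0.95^8 = 0.66 to 0.914^8 = 0.49.

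**What the trigger costs.** Assume a 50:50 binary moderator, 150 per arm (four cells of 75), an ACT effect that differs by 8 KOOS-ADL points between its levels, and an interaction test at 0.05. Power is Φ(8 / SE − 1.96).

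| Variance used | SE | Power if always tested |
|---|---|---|
| Within-workshop only, √(324 × 0.94 × 4/75) | 4.03 | 0.51 |
| Total, √(324 × 4/75) | 4.16 | 0.49 |
| Total × 1.30 | 4.74 | 0.39 |

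Under the trigger, the chance of both testing and detecting is roughly the product: 0.05 × 0.39 = 0.02 to 0.086 × 0.51 = 0.04.

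Low power is not the main cause. In the same simulation, a strong moderator (8 points per SD, interaction tested by ordinary regression) was detected in 97% of runs when always tested. It was both flagged and detected in only 4.7% (ICC 0) to 8.4% (ICC 0.06).

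**The case against.** **Other moderator statements exist.** A reader might infer that the imbalance clause is the plan's only provision on moderators. It is not. Sex and race/ethnicity results, week 1 data and surgery status are each addressed without an imbalance condition, so the point does not apply to them. They do not close the gap for the other variables: the first is descriptive, the second comes with no model, and the third is not one of the demographic or medical variables.

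**Moderation is not an aim.** This stands. None of the primary, secondary or exploratory aims asks who responds to ACT. The purpose rests on one sentence in an instrument description.

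**The clause may be mainly an adjustment rule.** A reader might also infer that balanced moderators can never be tested, or that the question cannot be answered. The documents do not support this. The clause governs the primary and secondary aim models, nothing prohibits other exploratory interactions, and the data are collected. What stands is narrower. The one inferential rule that names effect moderators for these variables selects them on the wrong criterion, which is more than missing detail.

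**Some variables will pass.** Also true. With 8 independent variables, the chance that at least one is flagged is 34% to 51%, and the clause covers more baseline variables than these 8. A prediction that the trial will report finding no moderators is therefore not supported. The set tested would still be a chance draw.

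**The remedy has limited yield.** Power is modest at 0.05, and falls to 0.24 to 0.32 at the plan's 0.0167 level (SE 4.74 and 4.16). Five variables by three primary measures by three time points would be 45 tests, with 45 × 0.05 = 2.25 false positives expected if no moderation existed. This is a good reason to restrict the analysis, not to select variables by imbalance.

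**Conclusion.** The point holds in limited form. For the demographic and medical variables, no intervention-by-variable analysis is specified, and the only stated inferential route to treating them as effect moderators depends on an observed arm difference. Under that rule a given true pre-randomisation moderator would be tested about 5% to 9% of the time.

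That range assumes a two-sided 0.05 screen and a baseline ICC of 0 to 0.06; an ICC of 0.10 would give 11%. It is an upper limit on testing as a moderator, since a flagged variable may be entered only as a covariate. It does not carry over to perioperative variables, which arise after allocation and could be shifted by the intervention. The power figures are illustrations that rest on an assumed effect difference and a 50:50 split.

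The sample size and the listed aims are not affected. The change is worth making because a stated use of the data is served by a rule that cannot serve it.

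**What to change.** In Data Analysis, remove the mention of effect moderators from the imbalance-triggered clause. Then add a statement along these lines: for a short list of pre-randomisation variables, chosen by the investigators before unblinding, an intervention × variable term will be fitted in the mixed model for every variable on the list, whether or not it differs between arms. Limit this to one time point (for example 6 months) or one overall interaction test per primary outcome. Report estimates with confidence intervals as exploratory, separately from the primary efficacy model.

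The cost is some wording and a few extra model fits on data already collected. Five variables by three primary outcomes (BPI Pain Severity, KOOS ADL, KOOS QoL) would be 15 tests, with 15 × 0.05 = 0.75 false positives expected if no moderation existed. Power is limited, so these results must be labelled exploratory and a wide interval must not be read as no moderation. The deletion also removes the moderator option in that clause for workshop-to-surgery time and perioperative variables. If the investigators want to examine those, a separate statement is needed that recognises they are measured after allocation.
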